8.3.3 Packaging and Labeling

The University of Utah Health Investigational Drug Service (UUH IDS) Pharmacy will prepare individual 1 g doses *Euphorbia kansui* extract powder or placebo using a Ohaus® Pharmacy Scale w/ Internal Calibration. As kansui (the root of *Euphorbia kansui*) is a Chinese herb with known safety issues, all laboratory and clinical personnel who handle kansui extract powder must use proper personal protection equipment (specifically - facemask, labcoat, and gloves) to prevent potential allergic reactions (e.g., contact dermatitis). Preparations will be packaged in white HDPE (high density polyethylene plastic) vials with screw caps and a tight, leakproof inner seal. Each study preparation bottle will be labeled with the required FDA warning statement, the protocol number, study participant number, a visit number, and directions for patient use.

Hunstman Cancer Hospital IDS
[name] [contact]

RX: xxxxx-x

Prescriber name

Date

Subject ID: xxxxxxxx

Protocol#: Kansui

Subject full name:

Mix 1 gram of powder in 4 ounces of warm water and ingest by mouth as directed. *Euphorbia kansui* extract powder or placebo.

Qty: 1 gram

Rt: oral Do not use after: "expiration date"

Refills: 0

Caution: Drug limited by Federal (United States) Law to investigational use only

8.4 Supply of Study Drug at the Site

8.4.1 Dosage/Dosage Regimen

One gram of *Euphorbia kansui* extract powder or placebo, reconstituted in 4 fluid ounces of warm water as tea, will be taken orally once daily for up to 3 days total. Participants enrolled in cohort 1 will be administered 1 g of *Euphorbia kansui* extract powder prepared as tea for a total of 1 day and participants in cohort 2 will be administered 1 g of *Euphorbia kansui* extract powder prepared as tea or placebo for 3 consecutive days during the study period.

8.4.2 Dispensing

All handling of the trial products, storage, reconstitution, individual dose preparation, and drug accountability will be done by the study investigators, delegated pharmacy staff, or delegated member of the study team.

8.4.3 Administration Instructions

Study Investigators will instruct study staff on how to prepare the *Euphorbia kansui* extract powder as a tea, per traditional Chinese medicine practice as outlined in the *Euphorbia kansui* Extract Tea Preparation Guidance SOP.

Study staff will dispense and observe study participant take 1 vial (1 g) of *Euphorbia kansui* extract powder in 4 mL of water prepared as follows:

- a. One gram of *Euphorbia kansui* extract from the labeled vial will be placed into a 6-ounce Styrofoam or paper cup.
- c. Four ounces of boiled water cooled to 170-185° F will be added to the powder in cup. Research staff will measure the water temperature using a designated thermometer for tea use only.
- d. The tea will be stirred for approximately 30 seconds using a wooden stirring stick.

- e. The tea will be allowed to cool for at least 5 minutes, reaching a temperature of less than or equal to 100° F, before administration.
- f. All contents in the cup will be checked to ensure that the powder and water have been stirred appropriately and fully consumed. Research staff will record the time of dose (Time 0) on the treatment flowsheet.
- g. Specific restrictions will be followed: no ice-cold beverages below <40°F) but graham crackers and room temperature juice will be allowed after the kansui dose (up to three servings of each), but other food & beverages will be restricted until AFTER 2+hr post-dose draw.

Study staff will then observe administration and side effects of participants on the day(s) of kansui treatment.

Study staff will similarly dispense and observe study participant take 1 packet of 100% pure decaffeinated black tea in 4 mL of water prepared as follows:

- a. One packet of Twinings English breakfast 100% pure black decaffeinated tea from the labeled vial will be place into a 6-ounce Styrofoam or paper cup.
- c. Four ounces of boiled water cooled to 170-185° F will be added to the tea in cup. Research staff will measure the water temperature using a designated thermometer for tea use only.
- d. The tea will be stirred for approximately 30 seconds using a wooden stirring stick.
- e. The tea will be allowed to cool for at least 5 minutes, reaching a temperature of less than or equal to 100° F, before administration.
- f. All contents in the cup will be checked to ensure that the tea and water have been stirred appropriately and fully consumed. Research staff will record the time of dose (Time 0) on the treatment flowsheet.
- g. Specific restrictions will be followed: no ice-cold beverages below <40°F) but graham crackers and room temperature juice will be allowed after the kansui dose (up to three servings of each), but other food & beverages will be restricted until AFTER 2+hr post-dose draw.

Study staff will then observe administration and side effects of participants on the day(s) of placebo administration as above for kansui treatment.

8.5 Supply of Study Drug at the Site

UUH IDS will package the study drug in HDPE vials and arrange for courier delivery directly from the UUH IDS Pharmacy to the University of Utah Center for Clinical and Translational Science (CCTS) located [name].

8.5.1 Storage

Euphorbia kansui extract powder storage will be in a cool, dry place, away from strong light, heat, or moisture. The shelf life is 2 years when properly stored with its original packaging. For this study, the vials of pre-measured 1 g doses of *Euphorbia kansui* extract powder will be stored in a locked cabinet in the UUH IDS Pharmacy. Entrance to the pharmacy is secure by electronic badge access, limited to IDS pharmacy personnel and managers. Temperature is controlled by air conditioning and monitored between 15-25 °C. A fully automated temperature monitoring system provides continuous temperature monitoring, recording, and notification. Temperature monitoring hardware accurately measure temperature and continually sends information to a web-based software system, which is accessible by IDS pharmacy personnel. Temperature records can be produced by authorized users for investigational refrigerator, freezer, or ambient temperature sensor through the temperature monitoring software system. If the temperature begins to go out of range, then the temperature monitoring software system will send a message to the on-call IDS pharmacist, who will respond within 15-30 minutes and take appropriate action to preserve the quality of the investigational product.

The UUH IDS will dispense study drug to the CCTS and maintain the distribution records. The CCTS Clinical Services Center (CSC) bionutritionist will administer study drug to participants and maintain the administration records.

8.6 Study Drug Accountability

An accurate and current accounting of the dispensing of study drug for each participant will be maintained on an ongoing basis by the study investigators. The number of study drug dispensed will be recorded on the Investigational Drug Accountability Record. The study investigators and CSC bionutritionist will verify these documents throughout the course of the study.

8.7 Measures of Treatment Compliance

Study participants will be monitored in the CCTS for directly observed therapy on the day(s) when *Euphorbia kansui* extract powder prepared as tea or placebo is administered. They will be receiving clinical and laboratory assessments on those days for up to 6 hours post-treatment.

9 STUDY PROCEDURES AND GUIDELINES

Prior to conducting any study-related activities, written informed consent and the Health Insurance Portability and Accountability Act (HIPAA) authorization must be signed and dated by the participant.

Eligible participants will receive a single dose for either a single or 3 consecutive days (Cohort 1: day 1; Cohort 2: days 1, 2, 3). Extensive sampling will occur before, during, and after the last dose. A full schedule of events for each cohort is provided below:

Study Events Table Cohort 1

Parameter	Day -14 ^a	Day -7 ^a	Day 1	Day 1	Day 1	Day 1	Day 2	Day 31	Early Withdrawal Visit (if applicable)
	Screen	Baseline	0 hrs ^b	0.5 hrs ^b	2 hrs ^b	4 hrs ^b	24-hr post-dose Follow-up		
Informed consent	X								
Questionnaires	X	X	X				X	X	X
Demographics	X								
Medical history, medications, AE	X	X	X				X	X	X
Vital signs	X		X		X	X	X	X	X
Physical exam (either Complete / Targeted) ^c	X		X				X	X	X
Study kansui administration			X						
Complete blood count w/diff	X		X	X	X	X	X	X	X
Comprehensive Metabolic Panel	X		X				X	X	X
Quantiferon test (QFT)	X								X
Pregnancy test (female participants)	X							X	X
Thyroid-stimulating hormone (TSH)	X								
Hep B Ag	X								
HCV Ab	X								
CD4+/CD8+ T cell counts	X	X	X				X	X	X
HIV RNA: standard assay	X	X	X				X	X	X
Immune activation (CD69, CD38, HLA-DR)	X	X	X	X	X	X	X	X	X
HIV reservoir measures	X	X	X	X	X	X	X	X	X
PBMC and plasma cryopreservation for future studies (PK, transcriptome analyses)	X	X	X	X	X	X	X	X	X

^a Days -14, -7, 4 and 31 represent the time from receiving the first dose of Euphorbia kansui extract powder prepared as tea on the Day 1 Visit.

^b Hours 0, 0.5, 2, and 4 represent time from receiving Euphorbia kansui extract powder prepared as tea dose on that dosing day.

^c The complete physical exam must occur at Screening. In the event of an Early Withdrawal Visit a complete physical exam is to be performed. A targeted physical exam is to be completed for all other time points.

Cohort 2. Participants in cohort 2 will be randomly assigned to either *kansui* or placebo first. The study will include a 56-day washout period between the two treatments (*kansui* and placebo). On study Day 88 a “second screening” visit for the second treatment assignment will occur; the second treatment phase will begin on study Day 102 and end on Day 132.

Study Events Table Cohort 2 (Treatment Phase 1)

Parameter	Day -14 ^a	Day -7 ^a	Day 1	Day 1	Day 1	Day 2	Day 3	Day 3	Day 3	Day 4	Day 31	Day 32-87
	Tx #1 Screening	Baseline	Tx #1 0 hrs ^b	0.5 hrs ^b	2 hrs ^b	4 hrs ^b	0 hrs ^b	0.5 hrs ^b	2 hrs ^b	4 hrs ^b	24-hr post-dose follow-up	56-Day Washout Period
Informed consent	X											
Questionnaires	X	X	X				X	X			X	X
Demographics	X											
Medical history, medications, AE	X	X	X				X	X			X	X
Vital signs	X		X		X	X	X		X	X	X	X
Physical exam (either Complete / Targeted) ^c	X		X				X	X			X	X
Study kansui administration			X				X	X				
Complete blood count w/diff	X		X	X	X	X	X	X	X	X	X	X
Comprehensive Metabolic Panel	X		X				X	X			X	X
Quantiferon test (QFT)	X											
Pregnancy test (female participants)	X											X
TSH	X											
Hep B Ag	X											
HCV Ab	X											
CD4+/CD8+ T cell counts	X	X	X				X	X			X	X
HIV RNA: standard assay	X	X	X				X	X			X	X
Immune activation (CD69, CD38, HLA-DR)	X	X	X	X	X	X	X	X	X	X	X	X
HIV reservoir measures	X	X	X	X	X	X	X	X	X	X	X	X
PBMC and plasma cryopreservation for future studies (PK, transcriptome analyses)	X	X	X	X	X	X	X	X	X	X	X	X

No Study Procedures During Washout

^aDays -14, -7, 4, 31, 88, 102-105, and 132 represent the time from receiving the first dose of treatment on the Day 1 Visit.

^bHours 0, 0.5, 2, and 4 represent time from receiving treatment (*kansui* or placebo) on that dosing day.

^cThe complete physical exam must occur at screening visits (Day -14 and Day 88). In the event of an Early Withdrawal Visit a complete physical exam is to be performed. A targeted physical exam is to be completed for all other time points.

Study Events Table Cohort 2 (Treatment Phase 2)

Parameter	Day 88	Day 102	Day 102	Day 102	Day 102	Day 103	Day 104	Day 104	Day 104	Day 105	Day 132	Early Withdrawal Visit (if applicable)
	Tx #2 Screening	Tx #1 0 hrs ^a	0.5 hrs ^a	2 hrs ^a	4 hrs ^a	0 hrs ^a	0 hrs ^a	0.5 hrs ^a	2 hrs ^a	4 hrs ^a	24-hr post-dose follow-up	
Informed consent												
Questionnaires	X	X				X	X			X	X	X
Demographics												
Medical history, medications, AE	X	X				X	X			X	X	X
Vital signs	X	X		X	X	X	X		X	X	X	X
Physical exam (either Complete / Targeted) ^c	X	X				X	X			X	X	X
Study kansui administration		X				X	X					
Complete blood count w/diff	X	X	X	X	X	X	X	X	X	X	X	X
Comprehensive Metabolic Panel	X	X				X	X			X	X	X
Quantiferon test (QFT)	X											X
Pregnancy test (female participants)	X										X	X
TSH												
Hep B Ag												
HCV Ab												
CD4+/CD8+ T cell counts	X	X				X	X			X	X	X
HIV RNA: standard assay	X	X				X	X			X	X	X
Immune activation (CD69, CD38, HLA-DR)	X	X	X	X	X	X	X	X	X	X	X	X
HIV reservoir measures	X	X	X	X	X	X	X	X	X	X	X	X
PBMC and plasma cryopreservation for future studies (PK, transcriptome analyses)	X	X	X	X	X	X	X	X	X	X	X	X

^a Hours 0, 0.5, 2, and 4 represent time from receiving treatment (kansui or placebo) on that dosing day.

9.1 Evaluations by Visit

A full schedule of events by visit is show above.

9.1.1 Screening Procedures

1. Participants will be consented by the study investigator, or properly trained and delegated coordinator, before any procedures take place. Eligibility will be confirmed and medical history and concurrent medications ascertained.
2. A complete physical exam and vital signs, including blood pressure, pulse, temperature, respiratory rate, and weight will be performed.
3. A detailed interview regarding past and current medical history, medications, substance abuse will be obtained.
4. Participants will complete the Baseline Questionnaires, which includes questions regarding general and HIV-specific medical history, previous and current medications or therapies, medication adherence, previous and intercurrent illnesses/conditions, hospitalizations, and minor lifestyle questions.
5. The full screening blood tests will be obtained:
 - a. Complete blood count (hemoglobin, hematocrit, red blood cell count, white blood cell count, white blood cell differential, and platelet count)
 - b. Comprehensive metabolic panel (serum sodium, potassium, chloride, bicarbonate, random glucose, blood urea nitrogen, creatinine)
 - c. Liver enzymes (aspartate aminotransferase [AST], alanine aminotransferase [ALT], alkaline phosphatase, total bilirubin, direct bilirubin)
 - d. Thyroid panel (thyroid stimulating hormone [TSH]) (Please note that for Cohort 2: TSH collected at the Screening Visit for Treatment Phase 1 but NOT collected for Treatment Phase 2)
 - e. Hepatitis B surface antigen and Hepatitis C antibody (Please note that for Cohort 2: Hep B and HCV Ag is collected at the Screening Visit for Treatment Phase 1 but NOT collected for Treatment Phase 2)
 - f. Quantiferon (QFT)
 - g. Plasma β -hCG (females only)
 - h. CD4+ and CD8+ T cell counts and plasma HIV RNA by clinical assay
6. Blood will also be collected for:
 - a. Immunophenotyping (CD69, CD38, HLA-DR expression on CD4+ and CD8+ T cells)
 - b. Latent HIV reservoir quantification (cell-associated HIV RNA, plasma HIV RNA). Given the potential for diurnal effect on the measures of HIV in resting cells, the first blood draw on this day will occur between 7:30 to 9:30 am.
 - c. Transcriptome analysis (RNA-seq)

9.1.2 Baseline Procedures

1. For eligible participants, a baseline visit will occur within 2 weeks of the screening visit and prior to day 1.
2. Concomitant medications and adverse events will be reviewed.
3. Baseline questionnaire will be re-administered.
4. Blood will be collected for:
 - a. CD4+ and CD8+ T cell counts and plasma HIV RNA by clinical assay
 - b. Latent HIV reservoir quantification (cell-associated HIV RNA, plasma HIV RNA. Given the potential for diurnal effect on the measures of HIV in resting cells, the first blood draw on this day will occur between 7:30 to 9:30 am.
 - c. PMBC (transcriptomics analyses) and plasma (PK analyses) storage

9.1.3 Dosing Day Procedures

1. For eligible participants, Day 1 will occur within 2 weeks of the screening visit. The 0.5, 2, and 4 hour visits noted below will occur within 30 minute windows. Participants will be free to leave the clinic in between the 0, 0.5, 2, and 4 hour visits.
2. 0 hours (prior to study drug administration that day)
 - a. History including concomitant medications and adverse event record
 - b. Follow-up questionnaires will be administered
 - c. Targeted physical examination & vital signs
 - d. Full blood examination (CBC, CMP)
 - e. HIV RNA: standard assay
 - f. Immune activation (CD69, CD38, HLA-DR expression on CD4+ and CD8+ T cells)
 - g. HIV reservoir: Given the potential for diurnal effect on the measures of HIV in resting cells, the first blood draw on this day will occur between 7:30 to 9:30 am.
 - i. Plasma HIV RNA (single copy assay)
 - ii. Cell associated HIV RNA (unspliced RNA) in CD4+ T-cells.
 - h. PBMC and plasma storage as below
3. 0.5 hours (after study drug administration that day)
 - a. CBC with differential
 - b. Immune activation
 - c. PBMC and plasma cryopreservation
4. 2 hours (after study drug administration that day)

- a. Vital signs
- b. CBC with differential
- c. Immune activation
- d. PBMC and plasma cryopreservation

5. 4 hours (after study drug administration that day)
 - a. Vital signs
 - b. CBC with differential
 - c. Immune activation
 - d. PBMC and plasma cryopreservation

9.1.4 Post-Dosing Days Procedures

1. No dosing will occur at the 24-hour follow-up visit following the last dosing day, nor on Day 31.
2. A history including concomitant medications, adverse event record and assessment of adherence antiretroviral therapy.
3. A physical assessment will occur as needed.
4. Vital signs will be obtained.
5. Follow-up Questionnaire will be re-administered.
6. Full blood examination including CBC, CHEM-7, and LFTs will be performed.
7. Samples will be collected for immunophenotyping (CD69, CD38, HLA-DR expression on CD4+ and CD8+ T cells), and for quantification of the latent HIV reservoir (plasma HIV RNA, cell associated HIV RNA in CD4+ T-cells). PBMCs and plasmas will be collected for future transcriptomics and PK analyses, respectively.

9.1.5 Early Withdrawal Visit

1. Record any Adverse Experiences and/or Review participant diary for adverse experiences and exclusionary medication use.
2. Record changes to concomitant medications.
3. Follow-up Questionnaire will be re-administered.
4. Perform complete physical examination, including recording of vital signs.
5. Collect blood for clinical laboratory tests (CBC, CHEM-7, LFTs)
6. Collect samples for immunophenotyping (CD69, CD38, HLA-DR expression on CD4+ and CD8+ T cells), and for quantification of the latent HIV reservoir (plasma HIV RNA, cell associated HIV RNA in CD4+ T-cells).
7. PBMCs and plasmas will be collected for future transcriptomics and PK analyses, respectively.

9.2 Clinical Assessments

9.2.1 Concomitant Medications

All concomitant medication and concurrent therapies will be documented at Screening/ Baseline, Study Treatment Day(s), at the 24-hour post dosing follow-up visits on Day 2 (for Cohort 1) and Days 4 and 105 (for Cohort 2), and Day 31 and 132. Dose, route, unit frequency of administration, and indication for administration and dates of medication will be captured.

9.2.2 Demographics

Demographic information (date of birth, gender, race) will be recorded at Screening.

9.2.3 Medical History

Relevant medical history, including history of current disease, other pertinent medical history, and information regarding underlying diseases will be recorded at Screening. Updated medical history including medication reconciliation and medication adverse effects will be recorded at Baseline, Study Treatment Day(s), at the 24-hour post dosing follow-up visits on Day 2 (for Cohort 1) and Days 4 and 105 (for Cohort 2), and Day 31 and 132.

9.2.4 Physical Examination

A complete physical examination will be performed by a study physician at Screening. Targeted physical examination will be performed on Study Treatment Day(s), at the 24-hour post dosing follow-up visits on Day 2 (for Cohort 1) and Days 4 and 105 (for Cohort 2), and Day 31 and 132.

9.2.5 Vital Signs

Body temperature, blood pressure, pulse and respirations will be performed after resting for 5 minutes at Baseline/Screening, Study Treatment Day(s), at the 24-hour post dosing follow-up visits on Day 2 (for Cohort 1) and Days 4 and 105 (for Cohort 2), and Day 31 and 132.

9.2.6 Questionnaires

Study questionnaires were developed in collaboration between UCSF and UCLA investigators for use in clinical trials evaluating the safety and efficacy of HIV cures. The questionnaires consist of a detailed interview, including medical history, current and previous medications/therapies, medication adherence, previous and intercurrent illnesses/conditions, hospitalizations, lifestyle, side effects, adverse events, etc. There is a baseline and follow-up version, both of which are completed electronically through the REDCap web application. The baseline/screening questionnaires require approximately 45-60 minutes to complete and the follow-up questionnaires require approximately 15-30 minutes.

9.2.7 Adverse Events

Information regarding occurrence of adverse events will be captured throughout the study. Duration (start and stop dates and times), severity/grade, outcome, treatment and relation to study drug will be recorded on the case report form (CRF). Criteria for participant management, dose interruptions, modifications, and discontinuation of treatment will be mandated only for toxicities attributable to kansui.

9.3 Clinical Laboratory Measurements

9.3.1 Basic Laboratory Measures

Blood will be obtained and sent to the San Francisco General Hospital clinical laboratory for complete blood count (hemoglobin, hematocrit, red blood cell count, white blood cell count, white blood cell differential, and platelet count), blood chemistry profile (serum sodium, potassium, chloride, bicarbonate, random glucose, blood urea nitrogen, creatinine), and liver enzymes (aspartate aminotransferase [AST], alanine aminotransferase [ALT], alkaline phosphatase, total bilirubin, direct bilirubin). At screening, additional laboratory measures will include Hepatitis B surface antigen and Hepatitis C antibody, thyroid panel (thyroid stimulating hormone [TSH]), quantiferon (QFT), and plasma β -hCG (females only).

9.5 Research Laboratory Measurements

9.5.1 HIV Clinical Laboratory Assay Measures

Blood will be obtained and sent to San Francisco General Hospital clinical laboratory for real-time determination of CD4+ and CD8+ T cell counts and plasma HIV RNA (viral load).

9.5.2 HIV Immunologic and Virologic Research Assay Measures

Blood will also be collected before, during, and after dosing to measure parameters of immune activation (CD69, CD38, and HLA-DR expression on CD4+ and CD8+ T cells) and to quantify the latent HIV reservoir (cell-associated HIV RNA [unspliced RNA] and plasma HIV RNA [single copy assay]). Given the potential for diurnal effect on the measures of HIV in resting cells, the blood draw for the 0-hour (zero hour) time point

(prior to first dose of kansui) will occur between 7:30 to 9:30 am on the screening, baseline, and treatment day(s).

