STATISTICS Primary Analysis Plan	[name] has expertise in epidemiology and biostatistics. She will be performing the data analysis for the study. Paired analyses using Wilcoxon signed rank tests will be performed to evaluate whether there is a statistically significant change in markers of immune activation (CD69, CD38, and/or HLA-DR) on CD4+ and CD8+ T cells after a 1 or 3 doses of Euphorbia kansui extract powder prepared as tea. Multivariate analyses will then be performed to evaluate the association between kansui and measures of immune activation at post-dosing, using linear mixed effects models, which account for within-participant correlation of observations and allows for greater stability in the estimate of the outcome measures within individuals. Similarly, for measures of the HIV reservoir, we will perform negative binomial mixed effects regression (a method to analyze over-dispersed count data) to compare the size of the latent HIV reservoir before and after kansui administration.
Rationale for Number of Participants	A total of 8 participants (2 from dosing cohort 1 and 6 from dosing cohort 2) will contribute to the analysis, with 8 or 25 timepoint measures, respectively. The within-individual variability will be reduced by use of the within-individual control measures, as well as the repeated measurements post-dosing. The primary outcome of the study will be an increase in the % T cell activation (CD38+ HLA-DR+) of CD8+ and CD4+ T cells. Based on our recent experience performing a phase 1 trial of canakinumab (an interleukin-1 beta inhibitor) to reduce inflammation in chronic HIV-infected ART-suppressed individuals, ¹ we estimate that we will have 80% power to detect a within-individual increase of 2.7 points in the % CD8+ T cell activation (standard deviation [SD] at 31 days of 1.6%). We will also assess virologic changes as secondary outcomes in the study. Based on data from our recent HIV latency phase 2b trial of disulfiram, ² we estimate that we will have 80% power to detect 0.6-0.7 log increases in cell-associated unsPLICED (CA-US) HIV RNA (SD=0.4 and 0.5 for Day 4 and Day 31, respectively), and a 0.6-0.5 log increases in ultra-sensitive plasma HIV RNA (SD=0.4 and 0.3 for Day 4 and Day 31, respectively).

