14 STATISTICAL METHODS AND CONSIDERATIONS

14.1 Data Sets Analyzed

[name] will be performing the data analysis for the study. Paired analyses using Wilcoxon signed rank tests will be performed to evaluate whether there is a statistically significant change in markers of immune activation (CD69, CD38, and/or HLA-DR) on CD4+ and CD8+ T cells after a 1, 2, or 3 doses of *Euphorbia kansui* extract powder prepared as tea compared to baseline (reference will be the average of the three baseline measures). Multivariate analyses will then be performed to evaluate the association between kansui and measures of immune activation at post-dosing, using linear mixed effects models, which account for within-participant correlation of observations and allows for greater stability in the estimate of the outcome measures within individuals. Similarly, for measures of the HIV reservoir, we will perform linear mixed effects regression to compare CA-US RNA levels before and after kansui and use negative binomial mixed effects regression (a method to analyze over-dispersed count data) to compare plasma HIV RNA levels before and after kansui administration (reference will be the average of three baseline measures).

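### The Day 31 and Day 132 reservoir draws have no set clock time, although the baseline they are compared with is fixed at 7:30-9:30 am

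*Combined protocol and SAP*

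**What the plan says.** The protocol gives its reason for a draw-time rule in section 9.5.2: "Given the potential for diurnal effect on the measures of HIV in resting cells". It sets the rule in four places.

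- Section 9.1.1 (screening, which also covers the second screening at Day 88): "the first blood draw on this day will occur between 7:30 to 9:30 am".
- Section 9.1.2 (baseline): the same window.
- Section 9.1.3 (dosing days, 0 hours): the same reason and the same window.
- Section 9.5.2 (summary): the 0-hour draw "will occur between 7:30 to 9:30 am on the screening, baseline, and treatment day(s").

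Section 9.1.4 covers the visits after dosing: "No dosing will occur at the 24-hour follow-up visit following the last dosing day, nor on Day 31". At these visits, "Samples will be collected for immunophenotyping (CD69, CD38, HLA-DR expression on CD4+ and CD8+ T cells), and for quantification of the latent HIV reservoir". It states no hour. The events table for Treatment Phase 2 of Cohort 2 schedules the same sampling at Day 132, again without an hour.

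For the analysis of cell-associated unspliced (CA-US) RNA and plasma HIV RNA, section 14.1 compares levels before and after kansui and says that the "reference will be the average of the three baseline measures". Section 14.4 repeats this. The synopsis (Rationale for Number of Participants) names Day 31 as one of two time points in its virologic power statement; for CA-US RNA it gives "SD=0.4 and 0.5 for Day 4 and Day 31, respectively".

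**The concern.** The protocol identifies a possible source of error and controls it on one side of the comparison only. Every scheduled pre-dose draw, in both phases, falls in a two-hour morning window. The Day 31 and Day 132 draws may fall at any hour, and section 14 has no term for time of day.

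Any systematic difference between morning and the usual hour of the late visits would therefore appear as a change after kansui. A higher value later in the day would look like latency reversal; a lower one could hide it. Section 4.1 expects small changes and has only eight participants to detect them, so a modest error matters. In Cohort 1 there is no placebo phase against which to check.

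**Working it through.** **Which draws the rule reaches**

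| Draw | Clock time in the protocol |
|---|---|
| Screening (Days -14 and 88) and baseline (Day -7) | 7:30-9:30 am |
| 0 hours on Days 1-3 and 102-104 (Cohort 2), Day 1 (Cohort 1) | 7:30-9:30 am |
| 24-hour follow-up (Day 2 in Cohort 1; Days 4 and 105 in Cohort 2) | None stated; loosely tied to morning through the dose time |
| Day 31, Day 132 | None stated |

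The visits with no tie at all to morning supply 1 of the 8 time points in Cohort 1 (Day 31) and 2 of the 25 in Cohort 2 (Days 31 and 132).

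**The plan's own Day 31 figures.** The synopsis pairs its values as Day 4 then Day 31. The Day 31 figures are thus 0.7 log with SD 0.5 for CA-US RNA, and 0.5 log with SD 0.3 for plasma RNA. The 0.6 log figures belong to Day 4.

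The test and significance level behind these figures are not stated. I assume a paired t-test, n = 6, two-sided 5%.

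- CA-US RNA: noncentrality = (0.7 / 0.5) × √6 = 3.43; power 78%, close to the stated 80%.
- Plasma RNA: noncentrality = (0.5 / 0.3) × √6 = 4.08; power 90%, above the stated 80%. With n = 5 it would be 79%. This does not affect the present point.

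**Bias if late visits fall at another hour.** The documents give no diurnal amplitude and no distribution of visit times. I assume a shift of 0.1-0.3 log for a visit outside the morning, and half of late visits outside it.

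Mean bias = 0.5 × shift. Share = mean bias / Day 31 detectable change. The last two columns give the chance of a significant result with no drug effect, from the same t-test with the mean shifted by the bias; the nominal rate is 5%.

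| Assumed shift | Mean bias | Share of 0.7 log (CA-US) | Share of 0.5 log (plasma) | False positives, CA-US (SD 0.5) | False positives, plasma (SD 0.3) |
|---|---|---|---|---|---|
| 0.1 log | 0.05 log | 7% | 10% | 5.5% | 6.3% |
| 0.2 log | 0.10 log | 14% | 20% | 6.9% | 10.3% |
| 0.3 log | 0.15 log | 21% | 30% | 9.3% | 17.1% |

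At the extreme, if every late visit were shifted by 0.3 log, the false-positive rates would be 22% and 51%. Section 14 plans mixed models for these measures, so the t-test is only a stand-in that shows the order of size.

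**Noise if visit times vary haphazardly.** Let the time of day instead add an independent SD s of 0.1-0.3 log (again assumed). For CA-US RNA at Day 31 the SD becomes √(0.5² + s²), that is 0.51 to 0.58. Power for 0.7 log falls from 78% to 77% at s = 0.1 and to 66% at s = 0.3.

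**The case against.** The best defence is the crossover. Order in Cohort 2 is randomised and double-blind, and both phases have the same gap, so the hour of a late visit should have no systematic link to treatment. A reader might infer that placebo protects only when clock times match between phases. That is not so: in a kansui-placebo contrast the bias cancels in expectation, and a mismatch adds noise. The defence is sound as far as it goes. But sections 14.1 and 14.4 write the reservoir analysis as before and after kansui and do not spell out that contrast, and Cohort 1 has no placebo.

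Three wider readings are tempting and the documents do not support them.

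- *The whole before/after comparison is confounded.* The Cohort 2 draws at 0 hours on Days 2, 3, 103 and 104 are already inside the window, and the 24-hour visits are roughly tied to it.
- *The 0.5, 2 and 4 hour draws have the same fault.* The stated reason concerns HIV measures in resting cells, and section 9.1.3 lists no reservoir measures at those hours. The events tables do mark them there, but that is a separate mismatch. Dose times are also already limited by the 0-hour window in both phases, so tighter matching is a preference.
- *The immune activation results are exposed too.* The protocol gives no diurnal reason for CD69, CD38 or HLA-DR.

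It is also fair to say that the protocol speaks only of a potential effect, that latent HIV is the third objective, and that safety is primary. These limit the importance of the point but do not close the gap.

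**Conclusion.** The gap in the text is certain: the draw-time rule covers the baseline and omits Days 31 and 132, while section 14 compares the two. The consequence is conditional. It is bias if late visits fall systematically outside the morning, and lost power if they vary at random.

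On the stated assumptions the mean bias is 0.05-0.15 log, which is 7-21% of the Day 31 figure for CA-US RNA and 10-30% of that for plasma RNA. The amplitude, its direction and the share of visits affected are all assumed. The point concerns the virologic measures at the late visits, with the 24-hour visits as a lesser case. It does not touch the safety endpoint, and no figure in the plan changes. It is worth correcting because draws taken at the wrong hour cannot be reliably repaired by analysis in eight people.

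**What to change.** In sections 9.1.4 and 9.5.2, extend the existing 7:30-9:30 am window to the first draw at the 24-hour follow-up visits (Day 2 in Cohort 1, Days 4 and 105 in Cohort 2) and at Days 31 and 132. Record the clock time of these draws.

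The cost is a sentence or so in each section and slightly less flexible appointments. All of these visits and draws already exist, so nothing is added for participants.
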